5.2 EXCLUSION CRITERIA

An individual who meets any of the following criteria will be excluded from participation in this study:

1. For females: currently pregnant or planning to become pregnant
2. History of more than one ACL reconstruction
3. Post-operative complications that required additional surgical intervention
4. Hospitalization for any reason other than the ACL reconstruction in the last 3 months
5. Plans for additional surgical procedures in the next 12 months
6. Live greater than 60 miles from the research lab
7. Have limitations that would prevent them from attending the biofeedback training sessions
8. Motor neuron diseases, Parkinson's disease, multiple sclerosis
9. Severely impaired hearing or speech (patients must be able to respond to phone calls)
10. No access to a telephone
11. Participating in another ACL intervention outside of standard post-operative physical therapy
12. Attending post-operative physical therapy more than 2 times per week at the time of study enrollment.
13. Inability to understand or speak English (since this will be required for the patient-based intervention)
14. Other self-reported medical problem that would prohibit participation in the study
15. Other health condition or personal issue judged by a study team member or primary care physician to make the patient inappropriate for study participation
16. Knee extension moment limb symmetry index (LSI) greater than or equal to 90% at the time of the initial study assessment

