4.1 OVERALL DESIGN

Aim 1: Determine the impact of a biofeedback training program on decreasing asymmetrical vertical ground reaction forces, frontal plane knee range of motion and the peak knee extension moment, known risk factors for secondary ACL injuries.
We will test the hypothesis that our biofeedback program will decrease the risk of secondary ACL injury by improving loading and movement symmetry during the dynamic task of landing from a jump 6 weeks post intervention.

Aim 2: To demonstrate our ability to recruit, retain and determine patient compliance in completing a biofeedback retraining program. We will demonstrate our ability to recruit 40 ACL reconstructed patients and assess study retention and compliance.

Overview: The goal of this single site, pilot randomized clinical trial is to determine the impact of an innovative biofeedback training program on decreasing surrogate measures of secondary ACL injury risk in adolescent athletes. Movement and loading symmetry will be assessed using the limb symmetry index ($LSI = \frac{ABS[Surgical] - ABS[Nonsurgical]}{0.5(ABS[Surgical] + ABS[Nonsurgical])} * 100$)^{2,3,7,34} prior to (baseline) and at two time points following (immediately following training (efficacy), and 6 weeks after (durability)) the biofeedback training program (**Aim 1; Figure 1**).

40 adolescent ACL patients (20 control, 20 intervention) will be recruited. Subjects will be block randomized into either the control arm or the intervention arm at baseline. All intervention subjects will complete an in-person (no home exercises) biofeedback retraining program for 6 weeks (2 times per week) with a focus on improving both load and movement symmetry through the use of tactile and visual feedback (**Figure 1**), which has been reported to be an effective biofeedback intervention²⁶. Finally, this study will demonstrate our ability to recruit subjects, engage them in the novel biofeedback program, and retain them until study completion. The outcomes from **Aim 2** will inform future study designs.

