load. Subjects will be asked to stand with their feet shoulder width apart (one foot on each force plate) with their hands in front on them with the shoulder flexed to 90 degrees for counter weight. The foot width will be standardized to ensure that foot placement is consistent for both the squatting trials as well as during the biofeedback training. The subject will be asked to squat down until their thighs are parallel with the ground or until their heels begin to come off from the ground, whichever occurs first. A stool will be placed behind the subject and will be set to the height where the subject's thigh will be parallel to the ground if they sat down (stool will be placed at the height of the popliteal fold), so that the subject will know the deepest position they have to achieve. If the subject is able to achieve a squat position where the thigh is parallel to the floor they will be instructed to squat until they barely touch down on the bench and then slowly stand back up without transferring any weight to the bench. Subjects are asked to squat down and watch the change in load beneath each foot. After completing the first squat, subjects will be asked to complete all subsequent squats with the goal of keeping the bars level on the graph or maintaining equal within a $LSI \geq 90\%$ (symmetric) load on both feet. This process will be completed a total of 30 times (3 sets of 10 repetitions each) during each of the training sessions with the same goal each time of maintaining the bars at an equal level. This is a simple measure that subject can easily understand and that can be altered through biofeedback.²⁴

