Tactile feedback: The second set of exercises at each biofeedback session will be resisted squats. A subject will be asked to squat while an external force is applied to the side of the knee (Figure 3) requiring the subject to work against this resistance to maintain balance and complete the squat. The band will be placed on the surgical limb of each patient and will be pulled at approximately a 45 degree angle toward the contralateral side. Pulling the subject toward the non-operative limb (one that is typically displaying higher loads) will require the subject to pull toward the surgical limb and maintain good frontal plane position by resisting frontal plane valgus. This is a typical exercise utilized in the clinic to aid in equal weight bearing and active hip abduction. The squat position that will be used during these exercises will be the same as the squat position used in both the visual biofeedback task as well as during the biomechanical testing. The subjects will be asked to stand with their feet at the standardized width and again squat until they make contact with the stool that will be positioned behind them during the biofeedback session. Subjects will be asked to complete 30 tactile feedback squats (3 sets of 10 squats) during each of the biofeedback sessions.

ATTENTION CONTROL

The 6-week attention control group program will focus on providing educational information to the participants related to the clinical and sports expectations as they are released to return to sport. These participants will be asked to meet 6 times during the 6-week intervention time period. Three of these visits will be completed in person and three will be completed using an online educational module (6 sessions). The online sessions will be completed in week 1, week 3, and week 5 while the in person sessions will be completed during week 2, week 4, and week 6. The content of these sessions will focus on providing information on ACL reconstruction, athlete expectation as they return to sport, incidence and risk factors for secondary ACL injuries, as well as some suggestions on the gradual progression back into sport.

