Landing trial: Subjects will be asked to complete 10 trials of a vertical stop-jump task. During the vertical stop-jump task, subjects will run straight forward for up to 5 steps taking off on 1 foot, landing on 2 feet (one foot on each force plate), and taking off again on 2 feet.^{16,18,20,21} Prior to testing maximum jump height will be determine using a vertec. During testing, a ball will be hung above the force plates at 75% of the subject's maxmum jump height to provide a target during jumping. Subjects will be instructed to jump up and grab the ball and then come down bilaterally on the two force plates. No instructions will be provided on how to land or what to do with their arms to initiate the jump. The stop-jump task will be used to determine if the biofeedback intervention is effective at decreasing secondary ACL risk factors as these risk factors were determined during landing. Subjects will be allowed to practice the task between 3 and 5 times until they are comfortable with the movement. A minimum of 5 minutes' rest will be given between conditions to minimize the effects of fatigue. If the results of the baseline jumping assessment indicates that the subject has a limb symmetry index (LSI) of greater than or equal to 90%, which is indicative of limb symmetry during hopping in healthy subjects, he/she will be excluded from the intervention.

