9 STATISTICAL CONSIDERATIONS

9.1 STATISTICAL HYPOTHESES

All statistical analysis will be completed under the direction of [name]. Depending on the outcome, change (completion-baseline), or the value at completion will be assessed, and the statistical significance of the group differences can be assessed by a t-test or the non-parametric equivalent (2-sample Wilcoxon). Standardized differences will be calculated for the purposes of powering the subsequent clinical trial.

- **Primary Efficacy Endpoint(s):**
We will test the hypothesis that our biofeedback program will decrease the risk of secondary ACL injury by improving loading and movement symmetry (knee extension moment asymmetry) during the dynamic task of landing from a jump 6 weeks post intervention.

Movement and loading symmetry will be assessed using the limb symmetry index ($LSI = \frac{ABS[Surgical] - ABS[Nonsurgical]}{0.5(ABS[Surgical] + ABS[Nonsurgical])} * 100$)^{2,3,7,34} prior to (baseline) and at two time points following (immediately following training (efficacy), and 6 weeks after (durability)) the biofeedback training program.

- **Secondary Efficacy Endpoint(s):**
No hypothesis testing will be completed for the secondary endpoint as this is a pilot clinical trial and will be used to determine the best procedures to following when planning a subsequent multi-center clinical trial. Therefore, we will demonstrate our ability to recruit 40 ACL reconstructed patients and assess study retention and compliance.

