9.2 SAMPLE SIZE DETERMINATION

This is a pilot study, with the purpose of discerning parameter estimates for use in powering a subsequent multi-center clinical trial. To estimate statistical power for this pilot design, we consider a comparison of outcomes by group across time. Previous studies have not examined the knee extension moment limb symmetry index, therefore the difference in knee joint position and the knee extension moment will be employed as proxy variables in order to estimate statistical power for this pilot design. We considered a comparison of outcomes between pre- and post-intervention^{17,18} and side-to-side differences in ACL-R patients. (Table 4).¹⁵

Using 2-sided testing between groups based on previous results, we will need 14 patients overall randomized at 1:1 ratio assuming 80% power to detect a significant difference in the knee extension moment between the groups with $\alpha=0.05$.¹³ Therefore, with recruitment of 40 subjects (goal of retaining 30

Table 4: Sample Size Calculations (N=sample size per group)

	Pre-intervention	Post-intervention	Sample Size
Peak Knee Extension Moment ¹⁰	3.7 ± 0.9	2.4 ± 0.5	N=7
Peak Knee Flexion ¹⁸	88.8 ± 8.0	105.0 ± 5.6	N=5
	Control	Intervention	Sample
Knee Flexion Angle ¹⁸	83.5 ± 20.5	103.8 ± 16.3	N=15
Vertical ground reaction force ¹⁸	2.0 ± 0.4	1.6 ± 0.3	N=14

subjects through study completion), we are adequately powered to declare significance. Thus, while not the primary purpose of this experiment, we are adequately powered to declare significance between groups.

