9.4.2 ANALYSIS OF THE PRIMARY EFFICACY ENDPOINT(S)

The goal of the proposed study is to determine the impact of an innovative biofeedback training program on decreasing risk factors for secondary ACL injuries in adolescent athletes. Based on

previous work, the primary variable of interest and a surrogate for secondary ACL injury risk will be the knee extension moment limb symmetry index (LSI). The previously established movement asymmetry risk factors³² and therefore the primary measures of interest are the knee extension moment, vertical ground reaction force, and frontal plane knee range of motion. Symmetry between the operative and non-operative limbs in this study will be determined by calculating the limb symmetry index (LSI). Asymmetry in the peak knee extension moment has been identified as significant predictors of secondary ACL injuries (therefore reduction in this asymmetry will decrease the risk for secondary ACL injuries).³²

For **Aim 1** of this pilot study a within subject repeated measures assessment (ANOVA), as implemented under mixed models, will be used to determine if a clinical (LSI>90%) and/or statistical difference exists between the pre- and the two post-intervention time points (efficacy and durability) for the primary outcome of interest (knee extension moment asymmetry). Post-hoc testing will be completed for any variable that is determined to be statistically different.

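### The printed limb symmetry index puts perfect symmetry at 0, yet the entry screen, training target and clinical criterion treat 90% or more as symmetric

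*Combined protocol and SAP*

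**What the plan says.** Sections 4.1 and 9.1 print the same formula. Writing S and N for the absolute surgical and nonsurgical values, it is LSI = 100 × (S − N) / [0.5 × (S + N)].

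Four places then apply a 90% threshold:

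- Section 5.2, criterion 16, excludes patients with "Knee extension moment limb symmetry index (LSI) greater than or equal to 90% at the time of the initial study assessment".
- Section 6.1.1 (visual feedback) sets LSI of at least 90% as the squat-load target and labels it symmetric.
- Section 8.2 (landing trial) excludes a subject who "has a limb symmetry index (LSI) of greater than or equal to 90%, which is indicative of limb symmetry during hopping in healthy subjects".
- Section 9.4.2 names the knee extension moment LSI as the primary variable and will "determine if a clinical (LSI>90%) and/or statistical difference exists between the pre- and the two post-intervention time points".

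On the form of the outcome, section 9.1 says: "Depending on the outcome, change (completion-baseline), or the value at completion will be assessed". Section 9.4.2 specifies a repeated-measures mixed model and describes the goal as reducing asymmetry.

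**The concern.** A threshold of 90% can mean nearly symmetric only on a scale where symmetry is 100. The printed formula is centred on 0, and the document gives no second formula or conversion. The same index serves as the biomechanical entry screen, the primary variable and the clinical criterion, so the mismatch affects who enters the trial and how the result is read.

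The intent to exclude symmetric patients is clear from section 8.2. The realistic harm is therefore ambiguity: two people working from the same force-plate data could compute different indices and enrol or classify the same patient differently. Section 9.1 also plans standardized differences for powering the next trial, and these depend on which index is used.

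A second problem follows from the sign. If a patient moves from a surgical-limb deficit to a surgical-limb excess, completion minus baseline keeps growing after symmetry has been passed. It then no longer measures reduction in asymmetry.

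**Working it through.** **Inputs.** The formula comes from sections 4.1 and 9.1, and the 90% thresholds from sections 5.2, 6.1.1, 8.2 and 9.4.2. All patient values below are hypothetical illustrations; the document gives none on this scale.

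**Formula in terms of the limb ratio.** With r = S/N:

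- index = 100 × (r − 1) / [0.5 × (r + 1)]
- inverse: r = (1 + x/200) / (1 − x/200) for an index value x

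**Trying to reproduce the plan's threshold.** For x = 90, r = 1.45/0.55 = 2.64. Symmetry (r = 1) gives 0. The statement that 90% or more indicates symmetry cannot be reproduced on the printed formula. Taking the absolute value does not help: |index| ≥ 90 means r ≤ 0.55/1.45 = 0.38 or r ≥ 2.64, which picks out the most asymmetric patients.

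**Three readings of the index.**

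| r = S/N | Printed index | Ratio, 100 × r | 100 − absolute index |
|---|---|---|---|
| 0.5 | −66.7 | 50 | 33.3 |
| 0.7 | −35.3 | 70 | 64.7 |
| 0.9 | −10.5 | 90 | 89.5 |
| 1.0 | 0 | 100 | 100 |
| 1.2 | 18.2 | 120 | 81.8 |
| 1.5 | 40.0 | 150 | 60.0 |
| 2.64 | 90 | 264 | 10 |

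Applying the rule that 90 or more is excluded:

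- **Printed index:** no patient with a surgical-limb deficit is ever excluded, nor is a symmetric one.
- **Ratio:** every patient with r ≥ 0.90 is excluded, including r = 1.5, which is clearly asymmetric.
- **100 minus absolute index:** exclusion requires |index| ≤ 10, that is r from 0.95/1.05 = 0.905 to 1.05/0.95 = 1.105.

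The last two readings disagree at r = 0.9, 1.2 and 1.5.

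**Signed change.**

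- r from 0.7 to 1.0 (full recovery): 0 − (−35.3) = +35.3.
- r from 0.7 to 1.5: 40.0 − (−35.3) = +75.3. This is 75.3/35.3 = 2.1 times as large, although absolute asymmetry rose from 35.3 to 40.0.
- Index from −20 (r = 0.9/1.1 = 0.82) to +40 (r = 1.5): +60, although absolute asymmetry doubled.

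**Signed means in the mixed model.** Two patients at +40 and −40 average 0, the value for symmetry, while their mean absolute asymmetry is 40.

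**Sample size.** Table 4 is not affected. Section 9.2 uses proxy variables because "Previous studies have not examined the knee extension moment limb symmetry index".

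**The case against.** The strongest reply is that nobody would apply the literal reading. Section 8.2 makes the purpose of the screen plain, this is a single site with a trained technician, and the manual of operations or data management plan may fix the derivation. That is fair as to intent, and no misclassification has been shown. But an unseen manual cannot correct a formula that the protocol states twice, and knowing the intent does not choose between repairs that classify the same patient differently.

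Several narrower points are partly right:

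- Only sections 6.1.1 and 8.2 explicitly equate 90% with symmetry. Criterion 16 and section 9.4.2 take that meaning from them.
- The inequalities are literally one-sided. However, section 6.1.1 speaks of equal load within the threshold, so it remains open whether a surgical-limb excess should count as symmetric.
- Crossing zero is a possibility, not an established fact. The visual exercise aims at level bars. The tactile exercise is described thus: "Pulling the subject toward the non-operative limb (one that is typically displaying higher loads) will require the subject to pull toward the surgical limb". That passage concerns squat load rather than landing moment, and the document gives no rate of over-correction.
- The change score is only one permitted analysis. The mixed model in section 9.4.2 has the same weakness on a signed scale, because opposite asymmetries cancel.

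**Conclusion.** The concern holds. As written, the entry screen and the clinical criterion do not do what they are meant to do: +90 needs a surgical-limb value 2.64 times the other, a symmetric patient at 0 is not excluded, and a participant restored to symmetry cannot satisfy LSI above 90%. This follows from the printed formula alone and needs no outside assumption. The document does not show whether the formula or the thresholds are in error.

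The signed-change problem is also real, but its size in this trial is unknown. It depends on how many participants cross zero, and the figures above rest on hypothetical limb ratios. The planned sample size stands. This must be fixed, because one unreconciled scale governs eligibility, the primary endpoint and the clinical criterion.

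**What to change.** Reconcile sections 4.1, 5.2, 6.1.1, 8.2, 9.1 and 9.4.2 to one written LSI scale, and state for each threshold whether it is one-sided or two-sided around symmetry. The sponsor should confirm the eligibility cut-off and the training target; no value is proposed here.

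Pre-specify the primary endpoint as distance from symmetry: either the absolute value of the difference index or |100 − 100 × S/N|. State which, because they are not interchangeable. Ratios of 0.5 and 2.0 both score 66.7 on the first, but 50 and 100 on the second.

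The cost is a protocol amendment, which the Statement of Compliance says needs IRB approval before implementation, and a small change to the endpoint derivation. No new data are required, since the planned assessments already measure both limbs.

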3 OBJECTIVES AND ENDPOINTS

OBJECTIVES	ENDPOINTS	JUSTIFICATION FOR ENDPOINTS
Primary		
Determine the impact of a biofeedback training program on decreasing asymmetrical peak knee extension moment.	Peak Knee Extension Moment Symmetry	Peak knees extension moment asymmetry between the operative and non-operative side is a known risk factors for secondary ACL injuries and is therefore being used as the primary outcome to determine the ability of the biofeedback intervention to decrease a risk factor for secondary ACL injury risk.
Secondary		
To demonstrate our ability to recruit, retain and determine patient compliance in completing a biofeedback retraining program.	
 • Number of intervention sessions attended (compliance) • Number of missed biomechanical assessment time points (retention) 	This is a pilot clinical trial in which we need to determine both compliance with the biofeedback intervention as well as subject retention through the end of the study in order to appropriately plan for a future multi-center clinical trial.
Tertiary/Exploratory		
Determine the impact of a biofeedback training program on decreasing asymmetrical vertical ground reaction forces, frontal plane knee range of motion and the association between each of these measures and the change in the peak knee extension moment symmetry.	
Exploratory Endpoints:
 
 • Peak Vertical Ground Reaction Force Symmetry • Vertical Ground Reaction Force Impulse Symmetry • Frontal Plane Knee Range of Motion • Peak Knee Flexion Angle Symmetry • Peak Knee Flexion Angle • Peak Knee Valgus 	The peak knee extension moment is a known risk factor for secondary ACL injury risk, however, it is challenging to collect this measure in a clinical setting as it requires the collection of synchronized three-dimensional kinematic and kinetic data. Therefore, these exploratory endpoints will be assessed to determine their association with the change in symmetry in the peak knee extension moment. Through this analysis we hope to be able to identify additional measures to use in assessing this biofeedback intervention that will be more easily implemented in the clinical setting.

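### The limb symmetry index is signed and its 90% clinical criterion has no ceiling, so over-correction towards the surgical limb can score as more improvement than restored symmetry.

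*Combined protocol and SAP*

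**What the plan says.** Sections 4.1 and 9.1 give the same LSI formula, the only one in the documents: "ABS[Surgical] - ABS[Nonsurgical]}{0.5(ABS[Surgical] + ABS[Nonsurgical])} * 100". The absolute value is taken of each limb's measurement, not of the difference, so the index keeps its sign.

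Section 9.1 compares groups on change from baseline or on the value at completion. Section 9.4.2 fits a repeated-measures mixed model that "will be used to determine if a clinical (LSI>90%) and/or statistical difference exists between the pre- and the two post-intervention time points".

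The same 90% figure appears at entry. Exclusion 16 in Section 5.2 removes anyone with "Knee extension moment limb symmetry index (LSI) greater than or equal to 90% at the time of the initial study assessment". The landing-trial text in Section 8.2 repeats the rule and gives its meaning: "limb symmetry index (LSI) of greater than or equal to 90%, which is indicative of limb symmetry during hopping in healthy subjects". Section 6.1.1 also uses an LSI of at least 90% as the target for symmetric load in the visual-feedback squat. None of these places sets an upper limit.

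Section 3 states the risk factor without direction: "Peak knees extension moment asymmetry between the operative and non-operative side is a known risk factors for secondary ACL injuries".

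**The concern.** The trial's target is symmetry, so the further a patient is from equality in either direction, the worse the result should score. A signed index does not do this. It keeps rising as the surgical limb overtakes the other, and a criterion with only a lower limit never counts that against the patient.

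The arms also differ in a way that could matter. Only the biofeedback arm does the resisted squat that "will require the subject to pull toward the surgical limb"; controls receive education. If training carried some patients past equality, the signed analysis would record this as extra benefit in that arm. The pilot is meant to supply parameter estimates for a multi-center trial (Section 9.2), so a distorted effect size would be carried forward.

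**Working it through.** **Inputs.** The formula from Section 9.1, the 90% cut-off from Sections 5.2, 8.2 and 9.4.2, and nothing else. The documents report no LSI mean, SD or proportion above 90%, so there is no plan figure to reproduce. The sample size in Section 9.2 uses proxy variables and does not depend on the cut-off.

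**Formula.** With r = |surgical| / |nonsurgical|, the printed index is LSI = 200(r - 1)/(r + 1), and r = (200 + LSI)/(200 - LSI).

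| r | Printed LSI | Ratio x 100 |
|---|---|---|
| 0.77 | -26.0 | 77 |
| 0.90 | -10.5 | 90 |
| 1.00 | 0 | 100 |
| 1.11 | +10.5 | 111 |
| 1.30 | +26.1 | 130 |
| 2.64 | +90 | 264 |

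**Change score on the printed formula.** An index of -30 is r = 170/230 = 0.74, and +30 is r = 230/170 = 1.35. These are mirror images and equally asymmetric.
- From -30 to 0 (full restoration): signed change +30; absolute index falls by 30.
- From -30 to +30 (asymmetry reversed): signed change +60; absolute index changes by 0.
- From +30 to 0 (full restoration, surgical-dominant start): signed change -30; absolute index falls by 30.

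The signed change ranks the second patient above the first and scores the third as a loss.

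**Group mean.** Half the patients at -30 and half at +30 give a signed mean of 0, the value for perfect symmetry. The mean absolute index is 30.

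The signed and absolute analyses agree while every patient stays below 0. They part only where some patients are at or beyond equality.

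**The 90% cut-off, ratio reading (not defined in the documents).** A patient at 130% meets LSI>90% and would be excluded at entry as symmetric. A patient at 77% does neither, although the printed indices are +26.1 and -26.0.

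**The 90% cut-off, printed formula.** LSI reaches 90 only at r = 290/110 = 2.64. The mirror value of -90 (r = 110/290 = 0.38) is neither excluded nor counted. The rule is still one-sided, but a patient at r = 1.30 (+26.1) is eligible and does not meet the criterion.

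**Possible size, ratio reading, on assumed distributions.** Normal ratios after training, mean 90 to 100 and SD 15 to 25:
- Mean 90, SD 15: 50% exceed 90. (111.1 - 90)/15 = 1.41, so 8.0% exceed 111. Share of those meeting the criterion: 8.0/50 = 16%.
- Mean 100, SD 25: 65.5% exceed 90. (111.1 - 100)/25 = 0.44, so 32.8% exceed 111. Share: 32.8/65.5 = 50%.

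At baseline, with mean 70 and SD 15, (111.1 - 70)/15 = 2.74, so 0.3% exceed 111. With mean 80 and SD 25, (111.1 - 80)/25 = 1.24, so 11% do. A lognormal ratio with median 0.6 to 0.9 and log-SD 0.2 to 0.4 gives 0.1% to 30%. The spread comes from the assumptions.

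**The case against.** A reader might infer four stronger things. The documents do not support them.

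- **That ordinary over-correction is excluded at entry and counted as success.** This holds only if LSI is a simple ratio. On the one formula printed, it needs a surgical limb about 2.64 times the other.
- **That the plan credits the biofeedback arm with a success rate.** It does not. The 90% value is one half of an and/or phrase inside a mixed model; no responder rate, and no comparison of responders between arms, is planned.
- **That training causes overshoot.** Nothing in the documents shows it. Section 6.1.1 also has 30 visual-feedback squats per session aimed at level bars, and describes the resisted squat as an aid to equal weight bearing. Over-correction is more plausible in the biofeedback arm than in control, but that is all. In a group centred on equality, some patients will lie above 111% through ordinary variation.
- **That the entry rule is wrong.** Section 6.1.1 says the non-operative limb usually carries more load, and the band goes on the surgical limb. A one-directional entry rule could fit that intervention, though the documents do not say it was chosen for that reason.

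These objections limit the threshold argument. They do not touch the signed index, which follows from the printed formula alone and enters the continuous analysis of the primary endpoint.

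**Conclusion.** The point stands as a definitional gap in the primary endpoint. On the printed formula, reversing an asymmetry of 30 scores twice the gain of removing it, and opposite asymmetries cancel in a group mean. This bears on the change-score comparison in Section 9.1 and the mixed model in Section 9.4.2, and needs no assumption about the 90% scale. The consequences for the cut-off at ordinary levels of asymmetry are conditional on a ratio reading.

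How many patients would be affected is unknown. The percentages above are illustrations and not estimates. The effect at entry is probably small, because Section 6.1.1 expects higher load on the non-operative limb. If no patient crosses equality, the signed and absolute results coincide.

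**What to change.** 1. Reconcile Sections 4.1, 5.2, 6.1.1, 8.2, 9.1 and 9.4.2 to one LSI definition, with the 90% figure on that scale.
2. In the same edit, make the clinical criterion in Section 9.4.2 two-sided. The mirror of the protocol's own 90% is a ratio of 0.90 to 1.11, about -10.5 to +10.5 on the printed formula.
3. Run the Aim 1 comparison on the absolute index alongside the signed one. State beforehand that a signed gain without a fall in the absolute index will not be read as improved symmetry.
4. Report the number over-corrected (above the upper limit) by arm at each post-intervention assessment.
5. For exclusion 16 and the matching rule in Section 8.2, state whether the cut-off applies in one direction or both. No eligibility limit is proposed here.

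**Cost.** Wording and one derived variable; no new data and no change to the sample size. The absolute index is bounded at 0 and will be skewed, but Section 9.4.1 already allows transformation or nonparametric tests. Fewer patients may meet the clinical criterion.
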